We developed a web intervention that included many of the components found in successful internet interventions. We found significantly improved skin cancer risk behaviors among young adults in an RCT that enrolled almost 1000 participants from a consumer research panel 59. To our knowledge, this is the only empirically-tested internet intervention focused on skin cancer risk behaviors targeting young adults. The intervention (UV4.me) is individually-tailored, interactive, and multimedia based on Ritterband and colleagues' 60 model for online behavior change interventions and the Integrative Model of Behavioral Prediction 61, which includes background variables such as demographics; cognitive variables such as beliefs, attitudes, norms, and self-efficacy; intentions; and behavior. We also emphasized appearance concerns, which is a major factor associated with young adult tanning 62-64.

In addition to successful outcomes, approximately two thirds of eligible participants enrolled in the study and completed the baseline survey, two thirds randomized to UV4.me accessed the intervention, and two thirds completed the 3-month follow-up. Yet, we still have an opportunity to increase UV4.me implementation and impact. We propose to do this by enhancing recruitment and enrollment strategies as well as incorporating additional interactive features into the intervention (i.e., creating a mobile version, embedding incentives into the intervention, adding a behavior tracking and feedback feature, peer interaction component, and ongoing news updates). Features/strategies were chosen based on participant feedback, our data (e.g., attempted use of mobile devices), and reviews/models of effective e-Health interventions including for tobacco cessation, physical activity, weight loss, and nutrition 60,65-68 and online implementation strategies 69-72. Several enhancements are expected to improve reach, implementation, and behavioral outcomes simultaneously.

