Randomized Controlled Trial. RCT participants will complete a baseline survey focusing on exposure and protection behaviors that takes a maximum of approximately 15 minutes on average. The study statistician will create a randomization scheme to randomize enrolled participants on a 2:2:1 basis to either the UV4.me2, UV4.me, or the e-pamphlet condition, respectively. Participants will not be informed of the differences in the intervention conditions beyond that they will all be online skin cancer risk

reduction interventions. Participants will then be asked to complete follow-up assessments at 3, 6, and 12 months post-baseline.

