10.0 Off-Study Criteria

Based on our data, experience, the enhanced study procedures, and the consumer research panel's experiences with young adults, we anticipate attrition of approximately 20% at each time-point. For dropouts, the reason for attrition will be analyzed if available to search for evidence of informative missingness.

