Efficacy. We will compare demographics across randomization arms using chi-squares and ANOVAs for categorical and continuous data, respectively. The primary outcomes are baseline to 3-month changes in UV exposure and protection. We will use multivariable linear regression to compare the effectiveness of UV4.me2 with UV4.me, and UV4.me2 with the e-pamphlet. We will not compare UV4.me to the epamphlet because UV4.me compared to a control condition was established in the prior study. Covariates in these models will include study arm, recruitment month/season, US region, and demographic factors identified as significantly imbalanced across arms (confounders). Analyses will be performed separately for the two primary outcomes. Variance stabilizing transformations may be applied as needed. Hypothesis tests will be two-sided with a 1.25% Type I error to account for multiple testing (2 intervention comparisons x 2 outcomes). Based on our data, experience, the enhanced study procedures, and the consumer research panel's experiences with young adults, we anticipate attrition of approximately 20% at each time-point. With 1500 young adults at baseline, we anticipate collecting 3-month follow-up data from 1200 participants, with 240 from the e-pamphlet arm and 480 participants from each of the other arms. The means (SDs) of the baseline to 3-month changes in UV exposure and protection indexes from the prior study control arm were 0.34 (0.74) and -0.37 (0.90), respectively. Given these parameters, we will have 80% power to detect small standardized effect sizes of 0.22 between the UV4.me2 and UV4.me arms, and 0.26 between the UV4.me2 and the e-pamphlet. These correspond to small detectable differences between intervention arms of 0.16 and 0.19 in baseline to 3-month changes in UV exposure and protection indexes, respectively. We will be able to detect slightly larger differences when the UV4.me2 and e-pamphlet arms are compared (detectable differences - UV exposure: 0.20; protection: 0.24). Analyses will assume that missingness depends on observed data (i.e., missing at random; MAR) 141. For drop-outs, the reason for attrition will be analyzed if available to search for evidence of informative missingness. Baseline variables will be compared by whether participants drop out or not. Significant variables will be added to the model to strengthen our MAR assumption. As a sensitivity analysis, we will use a shared parameter model with the assumption of missing not at random 142. If large changes in parameter estimation are found, we will use the results from the shared parameter model.

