
13.2 Statistical Analyses for Secondary Aims

Maintenance. We will compare baseline to 6- and 12-month changes in UV exposure and protection across study arms. Tests will be two-sided with a 5% type I error for these secondary analyses. We anticipate having follow-up data from approximately 960 and 768 participants at 6- and 12-months, respectively. This will allow for 154 participants in the e-pamphlet arm and 307 in each of the other two arms at 12 months. Detectable differences with 80% power are presented in Table 3.

Implementation. Using BeHealth's Wasabi data management system, we will create a summary index representing how frequently and for how long participants are logged into the interventions and how many sections are completed and determine whether this index is associated with behavioral outcomes. Whether and when a user accesses the e-pamphlet will be noted. We have experience using Google Analytics "goals" to track how frequently individual pages within modules are accessed. We will ask participants about their satisfaction with the study/intervention and selected components (e.g., the enhanced features) both from within the interventions and a one-month follow-up inquiry. These implementation variables will also be linked to participant source (i.e., skin protection organizations, Google Adwords, Facebook ads, consumer research panel) when possible so that sources can be compared in terms of participant intervention implementation. We will use the methods described for Aim 2 to compare these utilization and satisfaction measures across study arms, and Spearman's correlation to measure the level of association between implementation metrics and longitudinal changes in UV exposure and protection indexes within and across study arms. Tests will be two-sided with a 5% type I error for these secondary analyses. We anticipate 1350 participants at 1-month follow-up (epamphlet = 270, others = 540). Whether individuals click into the pages with discounts and free samples from skincare companies will be noted. We will assess whether accessing more incentives within the interventions is associated with greater intervention utilization and better behavioral outcomes.

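### The stated 80% power rests on 80% retention at 3 months; the prior study kept about two thirds, and no figure in the protocol bridges the gap

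*Combined protocol and SAP*

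**What the plan says.** Section 4.3 will "randomize enrolled participants on a 2:2:1 basis to either the UV4.me2, UV4.me, or the e-pamphlet condition, respectively". Section 13.1 (Efficacy) plans the primary analysis from a baseline of 1,500 and states: "we anticipate collecting 3-month follow-up data from 1200 participants". It then gives the split by arm as "with 240 from the e-pamphlet arm and 480 participants from each of the other arms". From these counts it claims 80% power, at a two-sided alpha of 1.25% per test, for standardized effects of 0.22 (UV4.me2 vs UV4.me) and 0.26 (UV4.me2 vs e-pamphlet). In index points these are given as 0.16 for exposure and 0.19 for protection in the first comparison, and 0.20 and 0.24 in the second.

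The loss rate is introduced with four grounds: "Based on our data, experience, the enhanced study procedures, and the consumer research panel's experiences with young adults, we anticipate attrition of approximately 20" per cent at each time-point. Section 10.0 repeats it: "we anticipate attrition of approximately 20% at each time-point".

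Section 3.0 summarises the prior UV4.me trial. Approximately two thirds of eligible people enrolled, two thirds of those randomized to UV4.me opened it, and "two thirds completed the 3-month follow-up".

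**The concern.** The primary outcomes are changes from baseline to 3 months. The prior study's 3-month retention is therefore the most direct evidence the team has on how many participants will be analysed. That figure implies a loss of about one third, while the plan assumes one fifth and names its own data as the first reason. The other grounds (experience, enhanced procedures, panel experience) carry no numbers, and the plan shows no power at any other retention level.

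At stake is whether the 80% claim for the four primary tests can be relied on. If retention repeats the prior record, all four tests have less power than stated at the stated effects, and the 6- and 12-month counts shrink with them.

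**Working it through.** **Inputs.** Baseline N 1,500 and alpha 0.0125 two-sided (Section 13.1). Allocation 2:2:1, so 600/600/300 (Section 4.3). Planned attrition 20% (Sections 10.0 and 13.1). SDs of change 0.74 for exposure and 0.90 for protection (Section 13.1). Prior 3-month retention approximately two thirds (Section 3.0).

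**Formulas** (two-sample normal approximation). With arm sizes n1 and n2, SE = √(1/n1 + 1/n2) in SD units. Detectable effect at 80% power = (2.498 + 0.842) × SE = 3.339 × SE. Power at effect d = Φ(d/SE − 2.498).

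**The plan's own figures.** 1,500 × 0.80 = 1,200, split 480/480/240.

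- UV4.me2 vs UV4.me: SE = √(1/480 + 1/480) = 0.0645, so the detectable effect is 0.216 SD. Multiplied by the SDs, that is 0.160 and 0.194 index points.
- UV4.me2 vs e-pamphlet: SE = √(1/240 + 1/480) = 0.0791, so the detectable effect is 0.264 SD, or 0.195 and 0.238 index points.

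These match the stated 0.22/0.26 SD and 0.16/0.19/0.20/0.24 index points. At the rounded effects, power is 81.9% (d = 0.22) and 78.6% (d = 0.26).

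**At two-thirds retention.** 1,500 × 2/3 = 1,000, split 400/400/200.

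- UV4.me2 vs UV4.me: SE = √(1/400 + 1/400) = 0.0707. Power at 0.22 = Φ(3.111 − 2.498) = 73.0%. The detectable effect is 0.236 SD (0.175 and 0.213 index points).
- UV4.me2 vs e-pamphlet: SE = √(1/200 + 1/400) = 0.0866. Power at 0.26 = Φ(3.002 − 2.498) = 69.3%. The detectable effect is 0.289 SD (0.214 and 0.260 index points).

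At the unrounded effects (0.216 and 0.264 SD), both comparisons fall from 80% to 70.9%.

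**Range.** Section 3.0 also describes as two thirds two rates that Section 1.0 gives as 73% and 70%. The 3-month figure could be equally loose. I use 73% as the upper end and assume 65% as the lower.

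| Retention | Completers | Arms | Power at 0.22 | Power at 0.26 | Detectable at 80% power (SD) |
|---|---|---|---|---|---|
| 80% (plan) | 1,200 | 480/480/240 | 81.9% | 78.6% | 0.216 / 0.264 |
| 73% | 1,095 | 438/438/219 | 77.6% | 74.0% | 0.226 / 0.276 |
| 70% | 1,050 | 420/420/210 | 75.5% | 71.9% | 0.230 / 0.282 |
| 66.7% | 1,000 | 400/400/200 | 73.0% | 69.3% | 0.236 / 0.289 |
| 65% | 975 | 390/390/195 | 71.7% | 68.0% | 0.239 / 0.293 |

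**Later waves.** The plan's 960 and 768 are 1,200 × 0.80 and 1,200 × 0.80². Starting from 1,000 and keeping the 20% loss at each later wave gives 1,000 × 0.80 = 800 at 6 months and 800 × 0.80 = 640 at 12 months.

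**The case against.** The 20% is a forecast resting on four grounds, and the prior data are only one of them. Section 4.5 pays for each follow-up, with a bonus for completing them all and a raffle at each time-point. Section 4.3.1 says the in-site incentives are meant to support retention and adds a mobile version. Section 4.1 notes that consumer panels can guarantee data collection. Better retention than before is therefore argued, and the plan does not misreport the prior study. All of this stands. But none of it is quantified. The prior trial was itself recruited from a consumer panel, and the new one adds four other kinds of source with no retention figures.

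It is also fair that two thirds is approximate and its denominator is not explicit. That is why a range is needed, but every value in it leaves both comparisons below 80%. The over-recruitment of up to 5% in Section 16.0 replaces poor-quality baseline surveys and is no reserve against dropout.

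Three stronger readings are tempting and should be set aside.

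- A reader might infer a calculation error. There is none: the stated effects follow from the stated counts.
- A reader might see a contradiction in "We anticipate 1350 participants at 1-month follow-up", a 10% loss where 20% is stated for each time-point. Section 4.5 does pay for a 1-month assessment. But Section 4.3 sets the follow-up assessments at 3, 6 and 12 months, the counts 1,200, 960 and 768 apply 20% at exactly those waves, and 1,350 feeds no primary power figure.
- A reader might extend the one-third loss to every later wave. The prior figure is for 3 months only, so the documents give no basis for that.

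**Conclusion.** The point holds as a gap in justification and sensitivity. The claim of 80% power depends on a retention rate that the protocol's only reported 3-month figure does not support. At two-thirds retention the loss is about 9 points of power for each comparison: 81.9% to 73.0% at 0.22 SD, and 78.6% to 69.3% at 0.26 SD. Across the 65% to 73% range, the loss against the plan's own counts is roughly 4 to 11 points.

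The practical effect is moderate. At two thirds, the detectable differences grow by about 0.015 to 0.023 index points and remain small, and neither the conduct nor the analysis of the trial is affected. The figures assume equal attrition across arms and no precision gain from covariates. The later-wave counts also assume that losses after 3 months stay at 20% per wave.

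**What to change.** Keep 1,500 participants and revise the power paragraph in Section 13.1:

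1. Report power and detectable effects at about two-thirds retention (1,000 completers; 0.236 and 0.289 SD) beside the 20% attrition scenario, and say which is the planning case.
2. Cite the figure that supports 20%, or stop attributing it to the prior data here and in Section 10.0.
3. Carry the lower 3-month count into Section 13.2: about 800 and 640 instead of 960 and 768 if later waves still lose 20%, with the detectable differences recalculated to match.

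The cost is a rewritten paragraph and stated detectable effects that are slightly less favourable. No extra participants are asked for. For comparison, securing 1,200 completers at two-thirds retention would take 1,200 ÷ (2/3) = 1,800 at baseline.

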The PI developed a web-based intervention (UV4.me) that was found to significantly decrease UV exposure and increase skin protection behaviors among young adults in a randomized controlled trial (RCT) of nearly 1000 participants recruited from a consumer research panel. The intervention (UV4.me) is individually-tailored, interactive, and multimedia in nature, and based on the Integrative Model of Behavioral Prediction. Similar to other online trials, 73% of eligible individuals completed the baseline questionnaire, 70% who were randomized to the intervention accessed it, and 68% accessed it and completed at least one module. However, we have an opportunity to increase the engagement, implementation, and ultimately, the impact of UV4.me. We will do this by adding several key interactive features/strategies suggested by participants, our data, and supported by the literature (i.e., by creating a mobile version, adding incentives embedded in the intervention, a behavior tracking and feedback feature, peer interaction component, and ongoing news updates). This Hybrid Type 2 dissemination-effectiveness project's purpose is to implement the enhanced intervention (UV4.me2) with adults aged 18-25 years at moderate to high risk of developing skin cancer and evaluate the intervention's effectiveness in a sample recruited online through national dissemination to the general population. This project will use the RE-AIM framework to determine the reach, effectiveness, implementation, maintenance, and cost of UV4.me2.

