Enhanced UV4.me2: New features/strategies were chosen based on participant feedback from the original UV4.me grant (e.g., suggested strategies to make UV4.me more interactive), our data (e.g., number of mobile users who tried to access UV4.me), and reviews/models of effective e-Health interventions 65,66 and implementation strategies 69,70,72. Several enhancements are expected to improve reach, implementation, and behavioral outcomes simultaneously:

1. Mobile Site. A mobile version will likely improve reach directly because more people will have access and may improve effectiveness indirectly by facilitating ongoing implementation. The mobile platform will be developed for both Android and Apple devices.

2. Incentives. The enhanced UV4.me2 site will also offer incentives in the form of clickable coupons and links to free samples for sun protection products (e.g., sunscreen). Appropriately selected incentives generally reinforce behavioral implementation, retention, and health behavior change, including in online trials, especially among those initially least motivated and/or for behaviors that are not intrinsically enjoyable (e.g., applying sunscreen) 71,109-115. These incentives will be used to reinforce behavioral implementation, retention, and health behavior change.

3. Behavioral Tracking & Feedback. Users will be allowed to set goals and enter relevant behavioral events (e.g., sunbathing, indoor tanning, sunscreen use) over time and see them summarized graphically on the homepage and receive motivating feedback (e.g., "Great job, your tanning is going down over time!"). Behavior tracking and feedback are well-established empirically-supported behavior change techniques including for internet interventions 116,117. As with the original UV4.me site, participants will be able to set "alerts" to notify them (e.g., email, SMS texting) to remind them to work on their behavioral goals.

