4.4.2 Measures for Secondary Aims

Maintenance. Skin cancer-related behavioral outcomes (described above) will be assessed at 6 and 12 months. We will also assess maintenance of reach, intervention implementation, and cost over time.

Implementation. Using BeHealth's data management system, we will record whether, how frequently, and for how long participants logged into the interventions, how many sections are completed, use of the enhanced features, and whether these variables are associated with behavioral outcomes. Whether individuals click into the pages with discounts/free samples will be noted. Whether and when a user accesses the e-pamphlet will be noted as well. We will ask participants to give Likert ratings of their satisfaction with and perceived helpfulness of the study/intervention and selected components (e.g., the enhanced features) both from within the intervention and a one-month follow-up inquiry. The 4-item App Subjective Quality scale from the Mobile App Rating Scale will be used to assess satisfaction (a = .93) 135. We have experience using Google Analytics "goals" to track how frequently pages within modules are accessed. These implementation variables will also be linked to participant source (i.e., skin protection organizations, Google Adwords, Facebook ads, consumer research panel) when possible so that sources can be compared by participant intervention implementation.

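### The primary 3-month analysis supports its missing-at-random assumption with baseline variables only; logged use of the interventions and dropout by arm have no stated role

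*Combined protocol and SAP*

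**What the plan says.** Section 13.1 (Efficacy) compares 3-month changes in two indexes by linear regression and assumes MAR. On sample size it states: "With 1500 young adults at baseline, we anticipate collecting 3-month follow-up data from 1200 participants". That total divides into 480 for each UV4 arm and 240 for the e-pamphlet. One loss rate is given for everyone: "we anticipate attrition of approximately 20% at each time-point".

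The section gives dropout three treatments:

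- Reasons for attrition are analysed where they are available (also section 10.0).
- For the model itself: "Baseline variables will be compared by whether participants drop out or not. Significant variables will be added to the model to strengthen our MAR assumption".
- A shared parameter model under MNAR is the sensitivity analysis. Its results are used if the estimates change by a large amount, which is not defined.

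The text does not say whether the baseline comparison is made over all arms together or within arms, and it plans no comparison of dropout rates between arms.

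Section 4.4.2 says of use: "we will record whether, how frequently, and for how long participants logged into the interventions, how many sections are completed". For the e-pamphlet it records only whether and when the pamphlet is opened. Sections 4.4.2 and 13.2 relate use to behavioural outcomes, compare it across arms and link it to recruitment source. Neither relates it to dropout or brings it into the missing-data model. Section 13.2 also expects 1,350 participants at the 1-month inquiry, more than the 1,200 at 3 months.

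**The concern.** In a self-administered online programme, people who never open the site may well be the ones who do not return the survey. Section 1.0 reports for the earlier trial that "70% who were randomized to the intervention accessed it", so about 30% did not. Hypothesis 4 expects greater use to go with better behavioural outcomes. It says nothing about dropout, so a link between non-use and dropout is plausible but not documented.

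If that link exists, missingness depends on something that the trial observes and the model leaves out. MAR given baseline covariates may then fail, while MAR given baseline covariates and logged use remains reasonable. Both primary contrasts would describe a more engaged group than the one randomised. A rule restricted to baseline variables cannot bring use in. Nor should use be added to the outcome regression, because it arises after randomisation and probably lies on the path to the effect.

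**Working it through.** **The plan's own figures.** Inputs from sections 4.3 and 13.1: 1,500 at baseline, 2:2:1 allocation, 20% loss, two-sided alpha 0.0125, 80% power. 1,500 × 0.80 = 1,200, split 480/480/240. Detectable effect d = (2.498 + 0.842) × √(1/n₁ + 1/n₂).

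- 480 against 480: 3.339 × 0.0645 = 0.216 (plan: 0.22).
- 480 against 240: 3.339 × 0.0791 = 0.264 (plan: 0.26).

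The stated figures reproduce. They treat loss only as smaller numbers.

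**Use-related dropout.** Access of 70% is the earlier trial's figure, applied here to both arms. Overall retention of 80% is the plan's. Retention by use and a benefit confined to users are assumptions. With r the retention of users:

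- retention of non-users = (0.80 − 0.70 r) / 0.30
- share of users among completers = 0.70 r / 0.80
- inflation = r / 0.80

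| Users retained | Non-users retained | Users among completers | Inflation | Estimate when the truth is 0.26 SD |
|---|---|---|---|---|
| 80% | 80% | 70% | 0% | 0.26 |
| 85% | 68% | 74% | 6% | 0.28 |
| 90% | 57% | 79% | 12.5% | 0.29 |

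The last row was simulated 2,000 times with 600 against 300 randomised and an effect of 0.37 SD in users, so the true effect is 0.37 × 0.70 = 0.259. The mean complete-case estimate was 0.291. Weighting users and non-users back to their randomised shares within arm gave 0.259. The standard errors were 0.079 (complete case) and 0.081 (access-stratified), a ratio of 0.081 / 0.079 = 1.025.

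**What a check over all arms together would miss.** Suppose that a baseline variable differs by 0.4 SD between dropouts and completers in one arm only. The pooled difference is 0.4 SD times that arm's share, with SE √(1/300 + 1/1,200) = 0.0645. Power is at two-sided 5%.

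| Arm affected | Pooled difference | Power, pooled | SE within arm | Power within arm |
|---|---|---|---|---|
| e-pamphlet (20%) | 0.08 | 24% | √(1/60 + 1/240) = 0.144 | 79% |
| UV4.me2 (40%) | 0.16 | 70% | √(1/120 + 1/480) = 0.102 | 97% |

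Missing the e-pamphlet variable has a limited effect. With 20% dropout and a correlation of 0.3 to 0.5 with outcome, the bias is 0.2 × 0.4 × 0.3 = 0.024 SD to 0.2 × 0.4 × 0.5 = 0.040 SD. In simulations with two arms of 600, a pooled check flagged a one-arm predictor (logit slope 0.4 to 0.6 per SD) in 79% to 98% of trials, and adjusting for it brought the bias to about zero. When the predictor acted in opposite directions in the two arms (slopes ±0.4), the pooled check flagged it in about 5% and a by-arm check in over 99%.

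**The case against.** The plan is not defenceless. Attrition reasons are post-baseline information, and the shared parameter model is the plan's answer to dropout that baseline covariates do not explain. A reader might infer that use-related dropout is bound to remain in the result. The documents do not support that, because the MNAR result can replace the MAR one. What remains is that reasons are used only where available and lead to no stated action. The shared parameter model is not said to depend on use or arm, its trigger is undefined, and its cited source is titled for longitudinal binary responses. It is no substitute for first using predictors that are already recorded.

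A reader might also infer that the baseline check is pooled. The text is silent on arm, so the firm statement is only that no by-arm step is given. The 24% figure applies to the smallest arm; the same difference in UV4.me2 gives 70%.

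Nor do the documents show that arm-specific dropout is to be expected. For the in-site coupons of UV4.me2 they say: "These incentives will be used to reinforce behavioral implementation, retention, and health behavior change". But section 4.5 pays for assessments, completion and first login in every condition, and section 13.1 projects the same loss in each arm. A different rate of loss by arm does not by itself bias the contrast; the loss must also be related to outcome beyond the model's covariates.

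Finally, the proposed auxiliary data are uneven. E-pamphlet records are thin. The 1-month inquiry is expected to miss 1,500 − 1,350 = 150 people; if nobody returns after dropping out, that is half of the 300 lost by 3 months.

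**Conclusion.** The point holds as a gap in the MAR analysis. The model can be strengthened only by significant baseline variables, logged use has no stated role in handling missing data, and no dropout comparison by arm is stated.

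The likely size is modest: 0% to 12.5% inflation, at most about 0.03 SD on 0.26 SD in the example, or roughly 0.4 of a standard error (0.03 / 0.079). That rests on 70% access in both arms, 80% overall retention, benefit only in users, and a retention split that the documents do not give. With equal retention it is zero.

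A reader might infer an excess of false positives. In this scenario there is none, because the bias is proportional to the true effect and vanishes under the null. It would arise if use-related dropout were confined to one active arm and users changed differently from non-users. With 40% to 70% of non-users retained and a user-to-non-user difference of 0.2 to 0.5 SD, the bias is 0.008 to 0.075 SD, and the 1.25% error rate becomes 1.3% to 9.1% for 480 against 480. Nothing in the documents supports those inputs, so they only mark out what by-arm reporting would reveal.

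The change is worth making before the data are analysed, because the better method is available with data already planned.

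**What to change.** In section 13.1, replace the significance-based rule with multiple imputation of the 3-month indexes, done separately by arm. Include the baseline indexes, demographics, recruitment source, the logged use available in that arm up to 3 months (for the e-pamphlet, whether and when it was opened), and the 1-month ratings where present. Then run the planned regression on all 1,500 randomised.

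State that use is an auxiliary variable in the imputation only and is not a covariate in the arm comparison. Keep the shared parameter model as the MNAR sensitivity analysis. Report retention, and baseline variables by dropout status, within each arm.

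The cost is SAP wording and modest programming, with no new data. The standard error may rise slightly (2% to 3% in the example), and the estimate may be less favourable than the complete-case one.

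### Section 13.1 lets the missing-not-at-random sensitivity model replace the MAR regression in the four primary efficacy tests, on a trigger that is not defined in advance

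*Combined protocol and SAP*

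**What the plan says.** Section 13.1 (Efficacy) names two primary outcomes: "The primary outcomes are baseline to 3-month changes in UV exposure and protection". Multivariable linear regression compares UV4.me2 with UV4.me and with the e-pamphlet, which gives four tests. On error it says: "Hypothesis tests will be two-sided with a 1.25% Type I error to account for multiple testing (2 intervention comparisons x 2 outcomes".

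On missing data, the same paragraph makes three statements in sequence:

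- Default: "Analyses will assume that missingness depends on observed data (i.e., missing at random; MAR". Baseline variables that differ between dropouts and completers are to be added to the model in support of this.
- Sensitivity: "As a sensitivity analysis, we will use a shared parameter model with the assumption of missing not at random". The citation is reference 142.
- Switch: "If large changes in parameter estimation are found, we will use the results from the shared parameter model".

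Section 10.0 adds a review of why people left: "For dropouts, the reason for attrition will be analyzed if available to search for evidence of informative missingness". Section 13.1 repeats this. Neither section makes the review the trigger for the switch.

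**The concern.** A sensitivity analysis that can take over the headline is a conditional primary analysis. Four things needed to make that condition reproducible are absent from the document:

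- how large a change must be;
- which parameter is compared (the arm contrast, its standard error, or another coefficient);
- whether a switch applies to one test, one outcome or all four tests;
- how the shared parameter model is built (visits used, shared random effect, dropout model).

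The citation does not fill the last gap. The title of reference 142 is about logistic models for binary responses, whereas the plan treats the UV exposure and protection indexes as continuous.

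The same gap between two fits could thus be called large or not large by people who already know what each choice does to significance. A gap also cannot carry the inference placed on it. It shows that the conclusion is sensitive to an assumption the observed data cannot test. It does not show that the MNAR model, or the MAR model, is the right one.

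**Working it through.** **Inputs from section 13.1.** SDs of change are 0.74 (UV exposure) and 0.90 (protection). Completers at 3 months are 480 (UV4.me2), 480 (UV4.me) and 240 (e-pamphlet). Attrition is 20%. Two-sided alpha is 1.25% per test and power is 80%. Hence z = 2.4977 for alpha, z = 0.8416 for power, and the sum is 3.3393.

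**Step 1. Reproduce the plan's figures.** SE = SD × √(1/n₁ + 1/n₂), and detectable difference = 3.3393 × SE.

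| Comparison | Outcome | SE | Detectable difference | Plan states |
|---|---|---|---|---|
| UV4.me2 v UV4.me | UV exposure | 0.0478 | 0.1595 | 0.16 |
| UV4.me2 v UV4.me | Protection | 0.0581 | 0.1940 | 0.19 |
| UV4.me2 v e-pamphlet | UV exposure | 0.0585 | 0.1954 | 0.20 |
| UV4.me2 v e-pamphlet | Protection | 0.0712 | 0.2376 | 0.24 |

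The figures agree, and 4 × 1.25% = 5%. The plan's alpha and power are sound for one fixed analysis per test.

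**Step 2. How far an estimate must move to change the conclusion (illustration).** Take an estimate exactly at the detectable difference and hold the SE equal in both models. Significance is lost once the estimate falls below 2.4977 × SE, that is, after a shift of 0.8416 × SE. In table order the shifts are 0.040, 0.049, 0.049 and 0.060 index units. As a share of the detectable difference this is 0.8416/3.3393 = 25.2%.

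If 20% are missing in each arm, the contrast moves by 0.20 × (dropouts' departure from MAR in one arm minus that in the other). The between-arm gap needed is therefore 0.0402/0.20 = 0.20, 0.0489/0.20 = 0.24, 0.0492/0.20 = 0.25 and 0.0599/0.20 = 0.30 index units, or 0.27 to 0.33 SD.

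**Step 3. Unequal SEs.** If the MNAR SE is r times the MAR SE, the margin in MAR SEs is 3.3393 − 2.4977 × r. At r = 1.2 it is 3.3393 − 2.9972 = 0.342, which is 10% of the detectable difference. It reaches zero at r = 3.3393/2.4977 = 1.34. Beyond that, significance is lost with no change in the estimate.

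**Step 4. Type I error (illustration; these inputs are assumptions, not in the documents).** Take two estimators, both valid under the null, with correlation 0.7 to 0.9. Switch when they differ by at least c MAR standard errors, with c = 0.5 to 1.5.

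| Rule | Per-test error |
|---|---|
| One model fixed in advance | 1.25% |
| Mechanical threshold, equal SEs | 1.25% in every case |
| Mechanical threshold, MNAR SE 1.2 to 1.5 times larger | 1.3% to 2.1% |
| More favourable model always reported | 1.85% (correlation 0.9) to 2.2% (correlation 0.7) |

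**The case against.** The plan deserves credit for what it fixes. The default model is named, there is only one alternative, and the switch runs one way. A reader might infer that the model behind every primary result is open until the data are in. The documents do not support that: Reach is Primary Aim 1 and has its own binomial and goodness-of-fit tests, and within efficacy only the trigger is open. Fixing the direction still does not determine whether the switch occurs.

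The 25% margin is also not a measure of harm from this rule. It is a property of any test with 1.25% alpha and 80% power, it applies only to an estimate exactly at the detectable difference, and it holds only at equal SEs. At equal SEs a mechanical threshold produces no inflation at all. So the stronger reading, that the rule demonstrably inflates the type I error, is not supported. The 2.2% figure needs an analyst who always takes the more favourable model; the undefined wording permits that, but the plan does not state it as its rule. The illustration also assumes both estimators are valid under the null, which sets aside the informative dropout the rule is meant to address.

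Finally, disagreement between the fits does not vindicate MAR. If MAR fails, keeping the MAR result has its own error, which cannot be sized here. That is a fair argument for showing both results prominently. It does not justify leaving the choice between them undefined.

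**Conclusion.** The point holds for the four efficacy tests and should be fixed. As written, the plan's own rule makes the reported efficacy model depend on the results, through a judgement made with both arm contrasts in hand, while the stated alpha and power describe a single fixed analysis. This rests on the text and not on any simulated figure.

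The size is illustrative. A shift of 0.040 to 0.060 index units can decide significance for an estimate at the detectable difference, and less is enough if the MNAR SE is larger. Reasonable analysts could disagree on whether a shift of that size is large. The inflation of the type I error cannot be derived from the documents. The plan's power calculation is not in dispute.

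**What to change.** Preferred change to section 13.1 (Efficacy):

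1. Delete the switching sentence.
2. State that the MAR regression, with the planned baseline predictors of dropout, is the reported primary result for all four efficacy tests.
3. Report beside it either a shared parameter model for continuous outcomes specified in advance (visits, shared random effect, dropout model) or a delta-adjusted tipping-point analysis.
4. If the two disagree, describe the conclusion as sensitive to missing data.

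Acceptable alternative, if the sponsor wants to keep a switch: fix the numeric criterion, the parameter it applies to, its scope (one test or all four) and the full shared parameter model before outcome data are seen by arm.

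Cost: under the preferred change, one sentence removed and a short specification added. It needs no new data, and sample size, alpha and stated power stay as they are. The team gives up the option to change the headline model after seeing results. If MAR fails, the reported estimate is biased, and readers depend on the sensitivity analysis beside it to see that. The change does not settle the other data-dependent choices in the same paragraph (covariates chosen for imbalance, transformations, dropout predictors).
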